6.3 Statistical Methods

6.3.1 Baseline Data

Standard descriptive statistics will be used to compare baseline characteristics of the two groups, which may be different despite randomization in this small pilot study.

6.3.2 Efficacy Analysis

The primary analysis will be based on an intention to treat approach and will include all randomized subjects. Interpretation and analysis of downloaded saturation data throughout the study will be managed in two ways. Saturation data will be cleaned, processed, and analyzed weekly. This will allow real-time assessments in order to ensure that the oximeter is being applied routinely and sufficient usable data are available. In addition, the data will be analyzed to determine whether the participant is having SpO₂ below the target range that would necessitate either increase in flow or medical attention.

Generalized estimating equations will be used for continuous primary outcomes such as frequency of IH and growth and logistic models for binary outcomes. Models will be adjusted for potential confounders that are significantly different in bivariate testing, because differences may exist despite randomization due to small sample size. Variables that will be considered for inclusion in the model are gender, gestational age, birth weight, race, small size for gestational age, and severity of BPD. The remaining exploratory outcomes will be compared between groups with simple bivariate tests such as t-tests and χ^2 tests. Exploratory subgroup analyses will be performed to evaluate the effect of the intervention on the gestational age and severity of BPD strata. Lastly, we will test for PMA week-specific differences between study groups through regression models controlling for key covariates, and using adjustments to account for multiple testing across PMA weeks. Given the sample size of this pilot study, we will likely not have sufficient power to draw definitive conclusions in these exploratory analyses; however, these approaches to the data are likely to be valuable in planning future studies.

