3.2 Allocation to Treatment Groups and Blinding

Infants will be randomized to higher or lower oxygen saturation (SpO₂) target ranges. The randomization sequence will be determined in advance, stratified by gestational age (<27 and 27-29 6/7 weeks at birth) and severity of BPD (moderate or severe, see Table 3 below) and balanced in random blocks of 2 or 4 patients. Allocation will be concealed in sequentially numbered opaque envelopes. The envelope with the lowest number will be opened by study staff. This plan for allocation concealment and stratification by key biologic variables will protect the scientific rigor of the study. After randomization, study group assignments will not be blinded. Multiples will be randomized separately. The two target SpO₂ ranges in the current trial represent the middle and upper range of the currently accepted range of clinical practice in our center.

Table 3: Screening Definition of BPD

Level of respiratory support at 36 weeks PMA	Eligibility
Room Air	Not Eligible (No or Mild BPD)
<2 L nasal cannula and <30% oxygen*	Eligible (Moderate BPD)
<2 L nasal cannula and >=30% oxygen**	Eligible (Severe BPD)
>=2 L nasal cannula or any positive pressure	Eligible (Severe BPD)

* <30% but receiving supplemental oxygen (22-29%) for at least 12 hours per day
** >=30% for 12 hours or more per day

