3.3.2 Total Number of Study Sites/Total Number of Subjects Projected

Infants will be recruited from 3 neonatal intensive care units (NICUs): The Children's Hospital of Philadelphia (CHOP) NICU, the adjacent Hospital of the University of Pennsylvania (HUP) NICU, and Pennsylvania Hospital (PAH) NICU. All outpatient care will take place at CHOP. Up to 50 participants may be enrolled to reach our target sample of 42 patients with evaluable data.

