6.4 Sample Size and Power

No preliminary data about incidence of IH in infants with moderate or severe BPD are available. Therefore, our sample size is based on extrapolations from the existing studies. Rhein reported 8.2 +/- 11.5 events of 5 seconds or longer per hour (197 per day) at 36 weeks PMA.(8) Poets reported a median 88.4 events of 10 seconds or longer per day in the Canadian Oxygen Trial.(7) We assume that fewer than half of these will be longer events that meet our study definition of IH, and estimate that our study participants will have between 20-30 IH events per 8-hour period at baseline. We plan to recruit 42 participants with useable data, which will provide sufficient power to detect a relative reduction of 30% between the high and low SpO₂ target groups if the baseline rate is 30 events per 8 hours. Therefore, our target sample size is 42 children *with complete data*.

Mean weight at 36 weeks PMA based on the Olsen growth curves is 2.8 kg,(14) and mean weight at 6 months CA based on the WHO growth curves is 7.9 kg.(15) Therefore, we assume a mean growth of 5.1 kg in the higher SpO₂ group and less weight gain in the lower SpO₂ group. The target sample size of 42 children will provide >80% power to detect a mean difference in growth of 0.5kg between the two study groups.

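### GEE is planned for the primary outcomes with about 42 infants and no small-sample method; under software defaults the test would be mildly anti-conservative

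*Combined protocol and SAP*

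**What the plan says.** Section 6.3.2 (Efficacy Analysis) states: "Generalized estimating equations will be used for continuous primary outcomes such as frequency of IH and growth". The analysis set is broad: "The primary analysis will be based on an intention to treat approach and will include all randomized subjects". Adjustment is conditional. Six baseline variables are candidates (sex, race, birth weight, gestational age, being small for gestational age, BPD severity), and one enters only if it differs significantly between arms. The same section adds: "Exploratory subgroup analyses will be performed to evaluate the effect of the intervention on the gestational age and severity of BPD strata".

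On size, section 6.4 says "our target sample size is 42 children", and section 3.3.2 says "Up to 50 participants may be enrolled to reach our target sample of 42 patients with evaluable data". Section 3.2 describes randomization "stratified by gestational age (<27 and 27-29 6/7 weeks at birth) and severity of BPD" and "balanced in random blocks of 2 or 4 patients", which implies 1:1 allocation. It also randomizes multiples separately.

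The plan gives no working correlation, link, variance estimator, reference distribution, significance level or small-sample correction. It acknowledges the small sample in two places only: chance baseline imbalance (6.3.1 and 6.3.2) and low power in the exploratory analyses (6.3.2).

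**The concern.** The standard GEE sandwich variance, referred to a normal distribution, is a large-sample method. The independent unit is the infant, so more nights of oximetry do not enlarge the sample in the sense that matters here. With about 21 infants per arm the sandwich tends to underestimate the variance of the arm effect, and each infant-level covariate adds to the shortfall.

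At stake is whether the error rate and precision reported for the primary comparison are what they appear to be. Section 6.3.2 expects its analyses to inform later studies, and overstated precision would carry forward. Low power, which the plan does acknowledge, is a different problem. Because the trial is unblinded, it is also better to fix the estimator before outcome data are seen.

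**Working it through.** **Inputs from the documents.** 42 evaluable infants (6.4), so n = 21 per arm; at most 50 (3.3.2), so n = 25 per arm; three named time points for IH (5.2.1); two strata factors (3.2); six candidate covariates (6.3.2). **Assumed, because not stated:** two-sided 5% level, uncorrected sandwich variance, critical value 1.96.

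**1. The plan's own figure.** Section 6.4 claims more than 80% power for a 0.5 kg growth difference but gives no SD or level, so it cannot be reproduced. By the normal approximation at two-sided 5%, it needs an SD of at most 0.578 kg. For IH only sufficient power is claimed, with no number. This does not affect what follows.

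**2. Exact unadjusted case.** For infant-level means, normal data and an identity link, the sandwich variance is (n−1)/n times the unbiased variance. The true error is P(|t with 2n−2 df| > 1.96 × √((n−1)/n)).

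| n per arm | 1.96 × √((n−1)/n) | df | True error |
|---|---|---|---|
| 25 | 1.920 | 48 | 6.1% |
| 21 | 1.913 | 40 | 6.3% |
| 10 | 1.859 | 18 | 7.9% |

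Interval width relative to the correct one is 1.913/2.021 = 0.946 at 21 per arm, about 5% too narrow. At 10 per arm it is 1.859/2.101 = 0.885, about 12% too narrow.

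**3. Simulation under no effect, 21 per arm, without stratified allocation.** Independence working correlation, three visits, within-infant correlation 0.6, 1,200–2,500 runs per setting (Monte Carlo SE about 0.5–0.9 points). The identity-link settings were normal data and counts with coefficient of variation 0.5–1.4. Log-link settings used counts only; the pretest and six-covariate rows cover coefficients of variation 1.0 and 1.4.

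| Covariates | Identity link | Log link |
|---|---|---|
| None | 5.8–6.9% | 6.9–7.3% |
| Chosen by p < 0.05 pretest | 6.3–7.0% | 7.4–8.1% |
| All six forced in | 7.6–9.3% | 10.7–12.0% |

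A check with a standard GEE routine (exchangeable correlation, robust SE, no covariates, 800 runs) gave 6.0% for normal data and 6.6% for counts.

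**4. Simulation of the procedure as planned.** Stratified blocks of 2 or 4, p < 0.05 pretest, identity link, three visits, correlation 0.5, 8,000 runs per setting (Monte Carlo SE √(0.05 × 0.95/8,000) = 0.24 points).

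- With 42 infants, no covariate was selected in about 85% of trials, two or more in under 1%, and four or more never.
- Strata unrelated to outcome: 6.6% (normal) and 5.7% (skewed). A separate run gave 5.7–6.4%.
- Strata prognostic (assumed effects: 0.3 SD per SD of gestational age, 0.5 SD for severity): 5.1% (normal) and 4.5% (skewed). A separate run gave 4.9% (normal).
- With 50 infants: 4.1–6.3%.

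The prognostic case falls because stratified allocation balances the factors while a model that omits them does not credit that balance. The standard error is then too large, which offsets the sandwich bias.

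**5. After correction.** Kauermann-Carroll with a t reference and the stratification factors in the model brought error from 6.1–7.4% to 4.2–5.4%. Mancl-DeRouen with t and six covariates gave 2.1–3.5% across two sets of runs.

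**The case against.** The strongest reply is that the plan never says it will use an uncorrected sandwich, a normal reference or a 5% level, and promises no confidence interval for the arm effect. An analyst could apply a correction without departing from it. That stands: every error rate here is conditional on defaults. What remains is that the choice is open.

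Second, a reader might infer a 6–9% error rate. The upper part of that range requires four to six covariates in the model. The plan admits only those that differ significantly, and two of the six are themselves stratification factors, so they will seldom qualify. The documents do not support 9% as the expected figure. Under some plausible conditions there is no inflation at all.

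Third, a reader might infer that the strata analyses are badly invalid. No stratum sizes are given, the section does not say those analyses use GEE or separate fits, and it calls them exploratory and unlikely to be conclusive. The figure of about 8% rests on an assumed 10 per arm.

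Fourth, this is a pilot with no decision rule tied to the 5% threshold, and clinical outcomes, including growth, are exploratory (5.2.2, 6.2). That limits the consequence. It does not justify leaving the method open for a comparison the plan calls primary and for which it claims power.

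One uncertainty runs the other way. Separately randomized siblings could leave fewer independent clusters than infants; this was not simulated.

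**Conclusion.** The point holds as a modest gap in specification. With default GEE inference at two-sided 5% and about 42 infants, error for the planned pretest-adjusted analysis is roughly 5–6.5% with an identity link. It is somewhat higher with a log link or highly variable counts, and near or below 5% when prognostic stratification factors are left out of the model. It reaches about 7.5–10% only if all six covariates are forced in (up to 12.0% in the log-link count settings), which the plan does not describe. Unadjusted intervals would be about 5% too narrow, and raising the sample to 50 changes little (6.1% unadjusted).

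These sizes depend on the assumed level, variance estimator, within-infant correlation and outcome distributions. They do not show that the primary result would be misleading. They show that a cheap, standard safeguard is missing.

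**What to change.** In section 6.3.2, state that the GEE models will include the randomization stratification factors (gestational age group and BPD severity). State also that standard errors will use the Kauermann-Carroll small-sample correction, with tests and 95% intervals from a t distribution whose degrees of freedom equal independent clusters minus infant-level parameters. Siblings should count as one cluster.

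The two parts belong together: once prognostic strata are in the model, the accidental offset disappears and the sandwich bias is no longer masked. Mancl-DeRouen should not be offered as interchangeable, since it became clearly conservative with several covariates.

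Cost: two sentences and a software option or short routine. Approximate widening against uncorrected intervals is √(42/40) × 2.021/1.96 = 1.06 with intercept and arm only, and √(42/38) × 2.024/1.96 = 1.09 with the two stratification factors added, so roughly 6–10%. Some settings will be slightly conservative. Each further covariate reduces the degrees of freedom and widens intervals a little more.

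### The primary models adjust only for covariates that differ significantly at baseline, which leaves the model open until data are seen and almost always shuts out the two stratification factors

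*Combined protocol and SAP*

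**What the plan says.** Section 3.2 (Allocation to Treatment Groups and Blinding) randomizes infants "stratified by gestational age (<27 and 27-29 6/7 weeks at birth) and severity of BPD", giving four strata, "balanced in random blocks of 2 or 4 patients". It justifies the design by saying that "stratification by key biologic variables will protect the scientific rigor of the study".

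Section 6.3.2 (Efficacy Analysis) sets the analysis: "Generalized estimating equations will be used for continuous primary outcomes such as frequency of IH and growth", with logistic models for binary outcomes. Covariates are then chosen by a rule: "Models will be adjusted for potential confounders that are significantly different in bivariate testing". The reason given is chance imbalance: "because differences may exist despite randomization due to small sample size". The candidates "are gender, gestational age, birth weight, race, small size for gestational age, and severity of BPD".

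Both stratification factors are therefore on the candidate list, but nothing commits the analyst to including them. They reappear by name only in the exploratory subgroup analyses. The models by postmenstrual week control for covariates that are not named. The plan gives no significance threshold for the baseline tests and does not say which standard errors the GEE will use.

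**The concern.** The rule works against the design. Stratified blocking makes the arms nearly equal on gestational-age stratum and BPD severity, and a rule that admits only imbalanced variables then excludes those two. An analysis that ignores the strata treats the estimate as more variable than the design made it. Standard errors come out too large, intervals too wide and coverage off nominal, to the extent that the strata predict outcome.

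The rule also means the primary model is settled only after baseline data are in hand. Six candidates allow 2^6 = 64 models, and no threshold says which would be fitted. Group assignment is unblinded, so a data-dependent model is harder to defend.

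A related gap is the GEE standard error. With about 42 infants as clusters, uncorrected sandwich errors with a normal reference are too small, and that choice decides whether adding the strata gives a valid test.

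**Working it through.** **Inputs from the documents.** 42 evaluable infants, taken as 21 per arm (balanced blocks imply 1:1); two binary strata, blocks of 2 or 4 (section 3.2); six candidates (section 6.3.2); more than 80% power for a 0.5 kg growth difference (section 6.4).

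**Assumed, because not stated.** Two-sided 0.05 for all tests; share of outcome variance explained by the strata (R²) of 0, 10, 25 and 40%; about 57% of infants under 27 weeks and 60% with severe BPD, varied in checks.

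**1. The plan's own figure.** No SD is given, so the power claim can be neither reproduced nor refuted. The effect giving 80% power with 21 per arm is 0.886 SD (t test), so the claim implies a growth SD of at most 0.5 / 0.886 = 0.56 kg. The comparisons below use 0.886 SD.

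**2. Can the rule select a stratification factor?** With blocks of 2 or 4 the arms differ by at most 2 within a stratum, and BPD severity spans two gestational-age strata. A worst case with 26 severe and 16 moderate infants is 15 v 11 severe and 6 v 10 moderate:

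χ² = 42 × (15×10 − 11×6)² / (26 × 16 × 21 × 21) = 42 × 84² / 183,456 = 1.62, p = 0.20.

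With 34 severe and 8 moderate (19 v 15 and 2 v 6), χ² = 42 × 84² / 119,952 = 2.47, p = 0.12. Even these extremes miss 0.05.

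Simulation agrees. BPD severity was selected in 0 of 120,000 trials. In a separate set of six scenarios (42 or 50 infants, varying prevalences), each binary stratum was selected in 0 of 4,000 runs at 0.05 and in at most 0.43% at 0.20. Gestational age tested in weeks entered in 0-0.23% at 0.05. Without stratification each would enter in about 5%.

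**3. Is the model fixed?** At least one of the six candidates entered in 14-19% of trials at a 0.05 threshold, 28-34% at 0.10 and 52-57% at 0.20.

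**4. What omission costs, by formula.** Stratification cuts the sampling SD of the estimate by about √(1 − R²), but the unadjusted standard error does not fall with it. So:

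- reported SE too large by 1/√(1 − R²): 1.05, 1.15 and 1.29 at R² 10, 25 and 40%;
- effective critical value 2.021/√(1 − R²): 2.13, 2.33 and 2.61, so type I error (t, 40 df) is about 3.9, 2.5 and 1.3%.

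**5. What omission costs, by simulation** (10,000 trials per cell, six candidates tested at 0.05):

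| Strata R² | 0% | 10% | 25% | 40% |
|---|---|---|---|---|
| Type I error, plan's rule, model-based t | 4.9% | 4.2% | 2.6% | 1.3% |
| Type I error, strata fixed, model-based t | 4.7% | 5.3% | 5.1% | 5.1% |
| Power, plan's rule | 78% | 80% | 82% | 84% |
| Power, strata fixed | 79% | 84% | 89% | 95% |
| Reported SE, rule relative to fixed | +1% | +6% | +17% | +31% |
| Type I error, rule, uncorrected sandwich/z | 6.3% | 5.6% | 3.6% | 2.1% |
| Type I error, strata fixed, uncorrected sandwich/z | 6.7% | 7.4% | 7.1% | 7.2% |
| Type I error, strata fixed, Kauermann-Carroll and t | 4.7% | 5.3% | 5.1% | 5.1% |

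With a skewed outcome (gamma, coefficient of variation 1.4) the pattern was the same: rule 4.4/3.2/2.1/0.9%, strata uncorrected 6.4/6.5/6.9/6.6%, strata with Kauermann-Carroll and t 4.5/4.4/4.7/4.5%.

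**6. In kilograms.** With SD 0.56 kg the unadjusted 95% half-width is 2.021 × 0.56 × √(2/21) = 0.35 kg. Multiplying by √(1 − R²) gives about 0.33, 0.30 and 0.27 kg with the strata at R² 10, 25 and 40%.

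**The case against.** The strongest reply is that little is at stake. Stratified blocking has already secured the precision of the point estimate: at R² 20% its true sampling SD was 0.277 unadjusted and 0.275 with strata. With model-based errors the rule is conservative, so false positives do not rise. The size of the loss rests wholly on an R² the documents do not supply, and the largest figures need 40%. The power anchor is growth, which sections 5.2.2 and 6.2 call exploratory; no SD is available for IH. The simulations use one value per infant, whereas the trial will have weekly averages that may be incomplete. And this is a pilot.

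Most of this stands as qualification. The loss is in reported standard error, interval width and test power, not in the estimate itself. The magnitudes are indicative, and R² of 0-25% is the range to lead with.

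It does not rescue the rule. That the model is not fixed holds whatever the R². The rule governs the primary-outcome models, and section 6.3.2 groups growth with them; its low-power caveat covers only the exploratory analyses. Fixing the strata costs almost nothing if they prove unprognostic (79.8% v 79.9% power at R² 0 in a separate run). The reply is right that adding the strata alone, with uncorrected sandwich errors, would worsen type I error, which is why the two changes belong together.

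**Conclusion.** The concern holds and should be fixed. The covariate rule makes the primary model depend on the data and in practice excludes the two factors on which randomization is stratified. Nothing elsewhere in the plan puts them back.

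The effect is conservative under model-based errors; under uncorrected sandwich errors, the omission and the small-sample bias partly offset. No power figure in section 6.4 is contradicted. The cost runs from nothing, if the strata do not predict outcome, to about 7 power points and a 17% larger reported standard error at R² 25%. It rests on the assumed R², a 0.05 threshold for the baseline tests, assumed covariate prevalences and one summary value per infant. That the strata are almost never selected depends on none of the R² assumptions.

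**What to change.** In section 6.3.2, replace the selection rule with one fixed model for IH and for growth: arm, gestational-age stratum and BPD-severity stratum, whatever the baseline comparison shows. Drop significance testing of baseline differences as a way of choosing covariates.

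In the same change, specify small-sample-corrected robust standard errors with a t reference; Kauermann-Carroll is one suitable choice.

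For growth, weight measured at or before randomization may be added as a fixed covariate. Enrolment opens at 34 weeks, so the 36-week weight can fall after randomization and should not be used for this by default. The other listed candidates can move to a labelled sensitivity analysis.

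The cost is SAP wording and two degrees of freedom (three for growth if weight is added). No new data are needed.

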Secondary analyses of a large randomized trial comparing higher versus lower SpO₂ targeting for newborn extremely preterm infants (6) demonstrated that IH, and in particular events <80% for at least one minute, are common in this population between birth and at least 9-10 weeks of age. (7) The duration of time with SpO₂ <80% is associated with the combined outcome of death after 36 weeks or disability at 18 months, cognitive or language delay, motor impairment, and severe retinopathy of prematurity. Importantly, this effect is significantly stronger when IH occurs 9- 10 weeks after birth than when it occurs earlier. While the neonatal community has been striving to minimize events in the weeks prior to discharge, these data force us to evaluate the value of reducing IH throughout infancy. It is unknown whether infants with BPD continue to have IH after 36 weeks PMA or after hospital discharge, or whether ameliorating this with longer-term use of supplemental oxygen would improve outcomes of these high-risk infants. IH is an important and novel therapeutic target in BPD, and may be a key component of decisions regarding safe and appropriate use and weaning of supplemental oxygen.

A recent trial of late caffeine therapy enrolled infants who were at least 33 PMA and in room air. (8) The control group had an average of 8.4 episodes of intermittent hypoxemia (decline in SpO₂ by at least 5% from baseline to <90% and lasting at least 5 seconds) per hour at 35 weeks PMA, which declined to 3.0 events per hour at 39 weeks PMA. The total time spent with saturations <90%, <85%, and <80% declined dramatically between 35 and 39 weeks. The clinical relevance of these more minor IH episodes and periods of hypoxia have not yet been demonstrated.

Our study collaborators have developed a simple, low-cost device for the BPD STAR Trial that securely transmits oximetry data wirelessly from the home environment. This device will enable us to implement a novel approach to studying management and outcomes of BPD. This study will provide critical data about whether infants with BPD continue to have IH after discharge; whether targeting higher SpO₂ ameliorates IH; and whether this management strategy is associated with improved outcomes until 6 months of age.

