3.4.1 Inclusion Criteria

- 1) Patient at CHOP,HUP, PAH (including both inborn and outborn infants)
- 2) Pre-term males or females infants born at <30 0/7 weeks gestation
- 3) Current age 34 0/7 to 43 6/7 weeks postmenstrual age
- 4) Diagnosis of moderate or severe Bronchopulmonary Dysplasia (as above)
- 5) Infant has never been discharged to home from the hospital

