4.5 Concomitant Medication

The majority of infants at our center are discharged without caffeine therapy; clinicians will be encouraged to continue this practice because caffeine is likely to impact incidence of intermittent hypoxemia.(8) The study will not dictate diuretic use either in hospital or after discharge, but clinicians will be strongly encouraged to wean diuretics before oxygen.(11) Ultimately, however, this will be a clinical decision. Exposure to caffeine, diuretics, bronchodilators, steroids, and any other medications will be recorded throughout the study. The dates of administration, dosage, and reason for use will be included.

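### The IH model leaves out caffeine at randomization, and for study-period outcomes age at randomization, and admits any covariate only through a baseline significance test; the cost is precision, not bias.

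*Combined protocol and SAP*

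**What the plan says.** Section 6.3.2 (Efficacy Analysis) sets two limits on adjustment. The candidates are those "considered for inclusion in the model are gender, gestational age, birth weight, race, small size for gestational age, and severity of BPD". The entry rule is: "Models will be adjusted for potential confounders that are significantly different in bivariate testing". Randomization (Section 3.2) is stratified by gestational age at birth and BPD severity, and by nothing measured at entry.

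On caffeine, Section 4.5 (Concomitant Medication) gives the reason for discouraging it at discharge: "caffeine is likely to impact incidence of intermittent hypoxemia". It adds: "The majority of infants at our center are discharged without caffeine therapy". It also says: "Exposure to caffeine, diuretics, bronchodilators, steroids, and any other medications will be recorded throughout the study", with dates, dosage and reason.

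On age, Section 3.4.1 allows entry at "Current age 34 0/7 to 43 6/7 weeks postmenstrual age". Section 1.3 describes a late-caffeine trial: "The control group had an average of 8.4 episodes of intermittent hypoxemia" per hour at 35 weeks, "which declined to 3.0 events per hour at 39 weeks PMA".

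On outcomes, Section 5.2.1 compares IH at 40 weeks PMA and at 3 and 6 months corrected age, and reports percent of recording time below three thresholds over the study period. Sections 2.1 and 6.1 word the primary endpoints as incidence and total duration up to 6 months. Section 7.1 starts monitoring at randomization.

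**The concern.** Section 6.3.2 justifies adjustment by the differences that a small sample can leave despite randomization. Yet the one drug that the protocol names as likely to affect its primary endpoint cannot be used, although it is recorded for every infant. Nor can PMA at randomization, which follows from the birth date and gestational age collected at screening (Section 5.1.1). That age decides how much of the early, possibly high-IH period an infant contributes to any outcome averaged from randomization onward.

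The entry rule adds to this. A listed variable with no true imbalance passes a 5% test about one time in 20, however strongly it predicts IH. The stratification factors are balanced by design, so they will seldom pass at all. At stake are the precision of the IH and hypoxemia-duration contrasts and a reader's ability to judge whether a chance imbalance moved them.

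**Working it through.** **The plan's own figure.** Section 6.4 states that 42 evaluable infants suffice for a 30% reduction from 30 events per 8 hours (a difference of 9). It gives no SD, alpha or numeric power, so 42 cannot be reproduced, only back-solved. For 80% power, two-sided 0.05, 21 per arm: SD = 9 / [(1.960 + 0.842) × √(2/21)] = 10.4. This SD is used only to turn explained variance into power.

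**Caffeine.** The documents give neither an effect size nor the share treated at randomization. Assumed: share p = 0.2-0.5, IH ratio r = 0.5-0.7 (30-50% fewer events), residual SD of log IH 0.5-1.0.

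R² = p(1−p)(ln r)² / [p(1−p)(ln r)² + SD²]

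- Low end: p = 0.2, r = 0.7, SD = 1.0 gives 0.0204 / 1.0204 = 2%.
- High end: p = 0.5, r = 0.5, SD = 0.5 gives 0.1201 / 0.3701 = 32%.

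Power at 21 per arm with SD 10.4 × √(1−R²): 80% at R² = 0, 82% at 0.05, 84% at 0.10, 88% at 0.20.

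Size of chance imbalance:

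- A difference of 4 or more treated infants between two arms of 21 has binomial probability 0.17, 0.24 and 0.28 at p = 0.2, 0.3 and 0.5.
- If caffeine halves IH, an arm's mean is proportional to 1 − 0.5q, where q is the share treated. A 4-infant difference (4/21 = 0.19) centred on p then shifts the arm ratio by 10% (p = 0.2) to 12% (p = 0.5).
- With wider ranges (p = 0.1-0.5, 20-50% fewer events), a one-standard-error imbalance, √[2p(1−p)/21], shifts the ratio by about 2-10%.

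These figures apply while status at randomization still reflects exposure. Most infants go home without caffeine, so any gain falls mainly on the 40-week and study-period outcomes. If entry were uniform over the window, 3.86/9.86 = 39% of infants would enter after 40 0/7 weeks and have no 40-week value, so the powers above are optimistic for that comparison.

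**PMA at randomization.** Slope from Section 1.3: k = ln(8.4/3.0)/4 = 0.257 per week, about 23% lower each week. With uniform entry (assumed), SD = 9.86/√12 = 2.85 weeks, and the standard error of the arm difference is 2.85 × √(2/21) = 0.88 weeks.

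For an IH value at a fixed age, the entry date drops out. A null-effect simulation (between-infant SD of log IH 0.35, assumed) gives an SD of the log arm difference of 0.108 unadjusted and 0.109 adjusted: no gain.

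For a mean from entry t₀ to 66 weeks (6 months corrected age taken as 40 + 26 weeks), with IH falling toward a floor F:

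mean = F + (8.4 − F)[e^(−k(t₀−35)) − e^(−31k)] / [k(66 − t₀)]

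The table compares arms 0.88 weeks apart, centred on 38.5 weeks. The last column is the simulated SD of the log arm difference, without and with entry PMA in the model.

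| Floor | Later-entry mean / earlier-entry mean | Shift | SD, unadjusted / adjusted |
|---|---|---|---|
| 39-week rate (3.0) | 3.281 / 3.341 = 0.982 | 2% | 0.109 / 0.109 |
| 20% of 35-week rate | 2.030 / 2.105 = 0.964 | 4% | 0.113 / 0.109 |
| 10% of 35-week rate | 1.233 / 1.318 = 0.936 | 6% | not run |
| None | 0.437 / 0.531 = 0.823 | 18% | 0.221 / 0.109 |

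Averaged over randomizations, the shift is zero in every case.

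**The case against.** Several objections stand and limit the point.

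- **Age at entry is not age at measurement.** A reader might infer that the protocol itself says entry PMA changes IH. It does not. The rates in Section 1.3 are by age at measurement, in room-air infants, for drops below 90% lasting at least 5 seconds. The trial counts SpO₂ below 80% for 30 seconds, in infants with BPD. Section 1.3 calls IH after 36 weeks unknown in BPD, and Section 6.4 says no preliminary data exist.
- **The named IH comparisons are at fixed ages.** Entry PMA has no direct effect there. Late entrants may be sicker, because some wait for extubation, but the documents give no figure for this.
- **Large entry-age effects are tempting to quote.** Carrying the decline on to 44 or 48 weeks makes the study-period mean of an infant entering at 43 weeks 38% or 63% lower than that of one entering at 36. That compares two single infants on a slope extended beyond its data. It is not a difference between arms.
- **Chance imbalance is already in the standard error.** A reader might conclude that the primary result is biased; randomization rules that out on average. What remains is lost precision and conditional imbalance.
- **The recorded data are not wholly unused.** Medications at 3 and 6 months are part of resource utilization (Section 5.2.2), which is compared between groups (Section 6.2). Section 6.3.1 compares baseline characteristics, and Section 6.3.2 plans PMA-week-specific models. But those models are exploratory with unnamed covariates, and none of these adjusts the primary IH contrast.

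The objection that covariate choice in a pilot is mere preference does not fully stand. The protocol itself names caffeine as likely to affect the primary endpoint, and the significance gate is a weakness whichever variables are listed.

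**Conclusion.** The point holds in a limited form. Section 6.3.2 confines adjustment to six birth or severity variables behind a significance test. It omits caffeine at randomization and, for outcomes accumulated from randomization, PMA at randomization. The consequence is lost precision and unadjusted chance imbalance, not systematic bias.

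The size is uncertain. The caffeine R² of about 2-32% rests wholly on assumed prevalence, effect and residual SD. For entry PMA there is no gain at fixed ages. A one-standard-error imbalance moves a study-period ratio by 2-6% if IH levels off between the 39-week rate and 10% of the 35-week rate, and by 18% only with no floor, against a target effect of 30%. Those figures assume uniform entry and borrow a slope from a different population and event definition. Priority: CONSIDER.

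**What to change.** In Section 6.3.2:

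1. Prespecify gestational age and BPD severity (the stratification factors) and caffeine at randomization (yes/no) as covariates in the IH and hypoxemia-duration models, whatever the baseline tests show.
2. Add PMA at randomization (weeks) only for study-period outcomes: percent time below each threshold, and IH incidence if summarized up to 6 months.
3. Include PMA at measurement in any generalized estimating equation that pools weekly data; the section does not say whether it is in the model.
4. Tabulate caffeine exposure after randomization by arm, descriptively. Do not adjust for it: in an open-label trial it can respond to the assigned arm and to IH itself, so adjustment could introduce bias.

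This changes analysis wording only. Both values come from data already collected, though caffeine should be named in the inpatient data list (Section 5.1.2), where it is not mentioned. The cost is a few degrees of freedom out of about 40, which slightly widens the interval if the covariates prove uninformative.
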